4.3.2 FMP2.1/AS02A: the vaccine and its potential clinical development pathway

The WRAIR antigen. FMP2.1 is a lyophilized preparation of the ectodomain of the 3D7 clone of *P. falciparum* AMA1. FMP2.1 is comprised of 478 amino acids, 449 of which are derived from the merozoite surface protein AMA1 of the malaria parasite, *P. falciparum*, 3D7 clone. The protein is produced in and purified from *E. coli* bacteria at the BioProduction Facility of WRAIR. The gene encoding the FMP2.1 protein was chemically synthesized to contain an *E. coli*-optimized codon usage to encode the amino acids representative of the AMA1 protein of the 3D7 clone of *P. falciparum*. The purified antigen will be adjuvanted with AS02A (oil in water emulsion [SB62] + MPL + QS21). This candidate vaccine is intended to limit malaria morbidity and mortality, and possibly infection, by stimulating host immune responses against the apical merozoite antigen-1 of *P. falciparum*. FMP2.1/AS02A is being developed as a potential component of a multi-stage, multi-antigen vaccine compatible with the advanced malaria candidate RTS,S/AS02A and/or blood stage vaccines based on other recombinant AMA1 or MSP1 antigens.

4.3.3 Pre-clinical toxicity, safety and reactogenicity of FMP2.1/AS02A

Clinical grade lots of FMP2.1 protein have been administered to mice, guinea pigs, rabbits and rhesus monkeys. FMP2.1 has been administered to mice and rabbits in combination with AS02A and elicited an excellent immune response without any overt signs of ill health or unusual responses. FMP2.1, administered with or without AS02A, has undergone and passed General Safety Tests in mice and guinea pigs, as well as Pyrogen Tests in rabbits. In primate

Page 19 of 96 Version 17, DEAP/MRTC/MMVDU CONFIDENTIAL

studies, detailed clinical, biochemical, and hematological examinations revealed no significant local or systemic reactions in any of the animals. Rhesus monkeys receiving $1/3^{rd}$ dose levels or full dose levels of the vaccine (FMP2.1/AS02A) developed high titer antibodies to the AMA1 protein with normal hematological and biochemical laboratory tests. In addition, the FMP2.1/AS02A formulation was acceptably tolerated in the rhesus macaque at the highest target human dosage (50 µg) and administration schedule (0, 1, and 2 months) and elicited high antibody titers.

All Adverse Events were expected except the one SAE. Dose escalation was held until relationship of the SAE to vaccination could be established. Evaluation of the volunteer was completed and it was determined the event was not vaccine related. A final SAE report was submitted. No protocol revisions have been made in response to AEs.

Group	A = low dose	B = medium dose	C = high dose
Number of subjects	8	8	7
Total immunizations	22	22	19
Grade 1 reactions	11	20	26
Grade 2 reactions	6	17	21

Adverse Events by group are summarized below:

This study used 0.5 mL of AS02A for each dose level of FMP2.1. For reasons of simplicity of reconstitution and administration, it was decided to reduce the volume of AS02A

Page 21 of 96 Version 17, DEAP/MRTC/MMVDU CONFIDENTIAL

proportionate to the reduction of FMP2.1 antigen from the full dose in future trials. Thus for the present trial each vial containing 50 µg of FMP2.1 will be reconstituted with 0.5 mL of AS02A from a prefilled syringe as described in Section 9.2.1.

Clearly, three species of animal, including humans, immunologically responded to FMP2.1 in a fashion that results in the production of antibodies that have the functional capability to inhibit parasite invasion or growth in erythrocytes. This evidence supports the further testing of FMP2.1 in a field setting.

4.3.6 Preliminary immunogenicity data from AMA1/AS02A Phase 1 trial

Figure. Geometric mean anti-AMA1 antibody titer by ELISA (OD). Immunizations were administered on Days 0, 30 and 60. All three dose levels appear to be immunogenic. These results are preliminary as of May 2004 and final analysis will be completed after the trial ends in September 2004.

MAL-032 (FMP2.1) Study

- 3. 0.1mL = 10µl RTS,S + 0.1mL AS02A
- 4. $0.5mL = 50\mu I FMP1 + 0.5mL AS02A$
- 5. $0.5mL = 50\mu l FMP1 + 0.5mL AS02A$
- 6. $0.25mL = 25\mu l FMP1 + 0.25mL AS02A$
- N/A Not available

The experience of the use of the AS02A adjuvant in children to date arises from the clinical development of the RTS,S/AS02A vaccine. Two Phase 1 safety and immunogenicity studies evaluating 0.1 mL, 0.25 mL and 0.5 mL doses of RTS,S/AS02A have been conducted in Gambian children aged 1 to 11 years. A 0.5 mL dose of RTS,S/AS02A contains 50 μ g RTS,S, 50 μ g MPL[®], 50 μ g QS21 and 250 μ L SB62. Each study was controlled with Imovax[®] human diploid cell rabies vaccine.

Pain at the injection site was a frequent symptom across all study groups. The incidence of swelling increased with dose level. The majority of general solicited symptoms were mild to moderate in intensity and short lasting. In children aged 6 to 11 years headache was the most frequently occurring general solicited symptom in subjects receiving RTS,S/AS02A (any dose level). In the younger children (aged 1 to 5 years), the most frequently occurring general symptom in subjects receiving the 0.1 mL dose RTS,S/AS02A was fever, reported after 11% of doses compared to 26% of doses in the rabies control group. In subjects receiving 0.25 mL dose RTS,S/AS02A, loss of appetite was the most frequent symptom, being reported after 12% of doses, which compared to 20% of doses in the control group. In subjects receiving 0.5 mL dose RTS,S/AS02A, irritability/fussiness was most frequently reported, occurring after 27% of doses compared to 12% of doses in the control group. Grade 3 general solicited symptoms were infrequent in both studies and resolved or decreased in intensity within 24 hours.

Unsolicited symptoms were recorded with similar (6 to 11 year-olds) or lower frequency (1 to 5 year-olds) in the study vaccine groups compared to the control vaccine groups. The majority of unsolicited symptoms were mild to moderate in intensity and unrelated to vaccination.

Hematocrit values were generally low but comparable between study groups. Six children in the RTS,S/AS02A groups (one in 0.1 mL dose group, five in 0.25 mL dose group) experienced moderate anemia, defined as a hematocrit of 15% to 24% during the period to 30 days post Dose 3. There were no cases of anemia in the 0.5 mL or control groups. All these children had documented malaria episodes before or at the time that anemia was recorded.

All children were monitored for liver function. Among the 6 to 11 year-olds, two children in the RTS,S/AS02A groups experienced a transient rise in ALT levels judged not to be related to vaccination and not clinically relevant. In the younger children, increases in ALT levels from pre-vaccination were observed in two subjects in RTS,S/AS02A groups and two subjects in the rabies groups. Of these, only one case in the rabies control group was judged to be clinically relevant and vaccination was discontinued after Dose 1. No other clinically relevant abnormalities of hematological or biochemical laboratory parameters were observed.

In the interval to 30 days post Dose 3, 6 serious adverse events (SAEs) in total occurred. One SAE occurred in the 6 to 11 year old study; a case of bronchopneumonia was reported in a subject in the rabies control group. The event was not considered causally related to vaccination and the subject made a full recovery. Five SAEs were reported in the 1 to 5 year old study.

Page 25 of 96 Version 17, DEAP/MRTC/MMVDU CONFIDENTIAL

Among the RTS,S/AS02A recipients one subject suffered acute malaria with acute upper respiratory tract infection (0.1 mL dose) and one subject suffered cerebral malaria (0.25 mL dose). In the rabies control group three SAEs were reported: acute severe malaria with urinary tract infection and salmonella septicemia, bronchopneumonia with bronchial asthma and accidental death due to drowning. All SAEs were considered not to be related to study vaccines. Apart from the fatal SAE, all subjects made a full recovery and were not withdrawn from the study.

The RTS,S/AS02A (0.25 mL dose) vaccine was evaluated in a double blind, randomized, controlled Phase I study under a new schedule (0, 1, 2 month) in children aged 1 to 4 years in Mozambique. Subjects received RTS,S/AS02A (0.25 mL dose) or Engerix[™]-B hepatitis B vaccine (GSK Biologicals, Rixensart, Belgium). As previously observed, local reactions at the site of injection were common. Unlike the Gambian pediatric trial, where swelling at the injection site was the most frequently observed local reaction, pain was the most frequently observed reaction. Grade 3 swelling was reported after 23% of doses of RTS,S/AS02A (0.25 mL dose), but did not occur following administration of Engerix[™]-B. The incidence of swelling in the RTS,S/AS02A group decreased after Dose 2 of vaccine, but increased after Dose 3.

No other clinically relevant abnormalities of hematological or biochemical laboratory parameters were observed.

Page 26 of 96 Version 17, DEAP/MRTC/MMVDU CONFIDENTIAL

A total of four serious adverse events were reported, two in each group, during the period to one month post Dose 3. One subject in the EngerixTM-B group suffered *P. falciparum* malaria; a second subject suffered glomerulonephritis secondary to skin lesions. In the RTS,S/AS02A (0.25 mL dose) group, one subject suffered a febrile convulsion 15 days after the second vaccination and another subject suffered from bronchopneumonia. All SAEs were considered not to be related to study vaccines. All subjects made a full recovery and were not withdrawn from the study.

The FMP1/AS02A trials in Kenya and Mali remain blinded and data on AS02A safety and reactogenicity are not yet available from these trials. However, no vaccine-related SAEs have been reported from these trials as of March 2004.

In summary, these studies, with a large cumulative experience in both malaria-naïve and malaria-experienced participants, suggest that AS02A has a good safety profile.

4.3.8 Justification of 0, 1, 2 Month Schedule

The overall testing program of FMP2.1 aims at carrying out studies in children in subsequent trials. With this goal in mind, the present study uses a 0, 1, and 2 month immunization schedule anticipating that this schedule will be more amenable to eventual incorporation into the Expanded Programme on Immunization of the WHO.

4.3.9 Justification of the vaccine dosing regimen and development plan for vaccine

The clinical development of the candidate malaria vaccine AMA-1/AS02A will progress in four distinct steps; 1) a Phase 1 dose-escalation trial in malaria naïve adults (recently completed), 2) a Phase 1 dose-escalation trial in malaria-experienced adults (the current protocol), 3) a Phase 1 dose-escalation study in young children that will result in dose selection for an efficacy trial, and 4) an efficacy trial of the selected dose in the target pediatric population.

The emphasis of the initial Phase 1 adult studies in malaria naïve and malariaexperienced populations is to describe the safety and tolerability of the highest anticipated vaccine dose intended for pediatric use. Our recent experience for other candidate malaria vaccines containing 10, 25 or 50 μ g of antigen formulated in AS02A showed that 25 or 50 μ g was more immunogenic than was 10 μ g. Therefore, the initial AMA-1 dose for this safety study is 25 μ g, rather than 10 μ g.

4.3.10 Comparator Vaccine

4.3.10.1 Rationale for rabies comparator vaccine

Having a comparator vaccine is particularly useful in Phase 1 trials conducted in malariaendemic areas, since background immunity and natural exposure to malaria may make it difficult to interpret immunogenicity data. This is particularly a concern in this trial in a setting with seasonal malaria when transmission intensity will be increasing during the period when vaccine is being administered. Rising titers of antibody to AMA1 could be due to immunization or to natural exposure or both. The use of a control group will permit comparison of immune responses and will result in a clearer interpretation of serological results. While a placebo control group would accomplish this same end, using a vaccine that is beneficial to the subjects increases

Page 27 of 96 Version 17, DEAP/MRTC/MMVDU CONFIDENTIAL

the benefit to risk ratio, which is always relatively low in a Phase 1 trial. We have chosen to use rabies vaccine as the comparator for several reasons: 1) the dosing schedule is compatible with that of FMP2.1; 2) to be able to compare results directly with recent and ongoing studies of the FMP1/AS02A vaccine in Mali and Kenya that used rabies vaccine as a comparator; and 3) the available evidence supports a benefit for participants who receive rabies vaccine.

Rabies prevalence in Mali is not known but available data from the Ministry of Health's Division of Epidemiology suggest that the rabies burden is high. Approximately 1,500 dog bites were reported to public health officials in Bamako, the capital of Mali, from 1996 through 1999. The vast majority of the dogs are unvaccinated and in most cases the status of rabies infection is unknown. 124 heads of dogs were examined for evidence of rabies infection. Rabies infection was found in 34 (27%) heads; 7 cases were negative and there were no reported results for 74 cases (60%). These incomplete data allow us to estimate that approximately 30% of dogs that bite humans may be carrying and potentially transmitting rabies infection. In the Bandiagara district health center, approximately one case of human rabies is reported per year. This is likely a considerable underestimate of the true incidence of rabies cases given the general population's reliance on traditional healers and the relatively low utilization of the district health center. Of note, three dog bites were reported among the 40 study subjects during a recent Phase 1 trial of malaria vaccine FMP1/AS02A in Kenya that used the rabies vaccine as a comparator.

We initially planned to use Aventis Imovax rabies vaccine as the comparator but due to a recall and unavailability of this vaccine we will use Chiron RabAvert rabies vaccine which is considered by the CDC to be equally safe and efficacious, and which has been shown to be essentially interchangeable with the Imovax vaccine (i.e. an immunization series started with one vaccine can be successfully completed with the other).

When the RabAvert® rabies vaccine is administered according to the recommended immunization schedule (days 0, 7, 21), nearly 100% of subjects attain a protective titer. In two studies carried out in the US in 101 subjects, protective antibody titers >0.5 IU/mL were obtained by day 28 in all subjects. In studies carried out in Thailand in 22 subjects, and in Croatia in 25 subjects, antibody titers of >0.5 IU/mL were obtained by day 14 (injections on days 0, 7, 21) in all subjects (52-55).

High antibody titers have also been demonstrated with off-label immunization with rabies vaccines. Among participants in England, Germany, France and Belgium who received two immunizations one month apart, nearly 100% of the participants developed specific antibody and the geometric mean titer for the group was 10 IU (56-59). The proposed immunization schedule of 0, 1, and 2 months is therefore expected to be highly successful in conferring protective immunity against rabies among the control participants.

4.3.11 Safety of RabAvert® rabies vaccine

Local and/or mild systemic reactions may occur after injection of RabAvert® rabies vaccine but these are usually transient and do not contraindicate continuing immunization. Local reactions such as induration, swelling and reddening have been reported more often than systemic reactions. In a comparative trial in normal volunteers, Dreesen *et al.* (52;60) described their experience with RabAvert compared to a HDCV rabies vaccine. Nineteen subjects received RabAvert and 20 received HDCV. The most commonly reported adverse reaction was pain at the injection site, reported in 45% of the HDCV group, and 34% of the RabAvert group. Localized lymphadenopathy was reported in about 15% of each group. The most common systemic reactions were malaise (15 % RabAvert group vs. 25 % HDCV group), headache (10 %

RabAvert group vs. 20 % HDCV group), and dizziness (15 % RabAvert group vs. 10 % HDCV group). In a recent study in the USA (4), 83 subjects received RabAvert and 82 received HDCV. Again, the most common adverse reaction was pain at the injection site in 80% in the HDCV group and 84% in the RabAvert group. The most common systemic reactions were headache (52% RabAvert group vs. 45% HDCV group), myalgia (53% RabAvert group vs. 38% HDCV group) and malaise (20% RabAvert group vs. 17% HDCV group).

None of the adverse events was serious, almost all adverse events were of mild or moderate intensity. Statistically significant differences between vaccination groups were not found. Both vaccines were generally well tolerated. Uncommonly observed adverse events include temperatures above 38°C (100°F), swollen lymph nodes, and gastrointestinal complaints. In rare cases, patients have experienced severe headache, fatigue, circulatory reactions, sweating, chills, monoarthritis and allergic reactions; transient paresthesias and one case of suspected urticaria pigmentosa have also been reported. Human serum albumin (HSA) is present in RabAvert at concentrations less than 0.3 mg/dose. No type III hypersensitivity reactions have been observed with RabAvert. Serious systemic anaphylactic reactions or neuroparalytic events have been reported in association with RabAvert administration. Against a background of 11.8 million doses distributed world-wide 10 cases of encephalitis (1 death) or meningitis, 7 cases of transient paralysis including 2 cases of Guillain-Barré Syndrome, 1 case of myelitis, 1 case of retrobulbar neuritis, and 2 cases of suspected multiple sclerosis have been reported.

4.3.12 Rationale for double blind controlled design

A double-blind controlled dose escalation trial will allow assessment of vaccine safety in each of three groups, one group each to receive medium and full dose levels of the experimental vaccine, and one group to receive the comparator vaccine. Thirty adults will be randomized to receive the medium dose level of FMP2.1 (n=20) or rabies vaccine (n=10) and thirty to receive the full dose level of FMP2.1 (n=20) or rabies vaccine (n=10). The division of the rabies group into two groups of ten is done to maintain blinding at each immunization time point, and all participants who receive the rabies vaccine will be analyzed as a single group. The sample size of the groups, however, will not allow detection of anything other than very large differences in the occurrence of adverse events among the three groups. The advantage of double blinding is to remove the potential for investigator and participant prejudgment about the effects of the vaccines in the reporting of adverse events.

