7.1.2 Treatment allocation and randomization

Individual participants will be randomized to receive either full dose or half dose FMP2.1 or RabAvert[®] Rabies vaccine without stratification for gender. Participants will be randomized to two groups of 30 subjects (cohorts 1 and 2). The first 30 eligible volunteers will constitute the first cohort and will be randomized in a 2:1 ratio to receive 25µg of FMP2.1 adjuvanted with 0.25 mL of AS02A (n=20) or RabAvert[®] vaccine (n=10). Similarly, the next 30 eligible volunteers will constitute the second cohort (cohort 2) and will be randomized in a 2:1 ratio to receive 50ug of FMP2.1 adjuvanted with 0.50 mL of AS02A (n=20) or RabAvert® vaccine (n=10). Within each cohort, treatments will be assigned to subject ID numbers in randomized blocks. Randomization to either the two vaccines (FMP2.1/AS02A or RabAvert®) will be done using a computer-generated randomization list. The randomization list will contain sequential codes linking a study number to a vaccine assignment (FMP2.1/AS02A or RabAvert®). Study numbers will be assigned to participants of each cohort in the order in which they provide written informed consent to be enrolled in the vaccine trial. The vaccine and dose that are assigned during the first immunization will be maintained for second and third immunizations. Access to the randomization list will be exclusively limited to the study drug manager(s)/pharmacist(s), study statistician in Bamako, and statistical consultant in Baltimore. These individuals are unblinded and will not be involved in study participants' further evaluation. The Local Medical Monitor will also keep one set of the randomization code in a sealed envelope, in the event that emergency unblinding is required. The reason for any unblinding will be documented as well as the steps taken.

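### Section 7.1.2 calls dose level and cohort randomised, but both follow enrolment order; with rabies controls pooled, a cohort shift enters 50 v 25 µg in full and each dose v rabies by half

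*Combined protocol and SAP*

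**What the plan says.** Section 7.1.2 opens with "Individual participants will be randomized to receive either full dose or half dose FMP2.1 or RabAvert", followed by "Participants will be randomized to two groups of 30 subjects (cohorts 1 and 2". The allocation rule in the same paragraph differs: "The first 30 eligible volunteers will constitute the first cohort and will be randomized in a 2:1 ratio", to 25 µg (n=20) or rabies (n=10), and "the next 30 eligible volunteers will constitute the second cohort (cohort 2", split 2:1 between 50 µg (n=20) and rabies (n=10). It adds that "Study numbers will be assigned to participants of each cohort in the order in which they provide written informed consent".

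Sections 4.3.12 and 6.1 describe randomisation only within each set of 30, which matches the allocation rule and not the opening sentences. Section 4.3.12 gives blinding as the reason for splitting the rabies recipients 10 and 10, and states that "all participants who receive the rabies vaccine will be analyzed as a single group".

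Section 6.1 places each 50 µg immunization at least 14 days after the matching 25 µg one and sets no upper limit. Section 4.3.10.1 expects that "transmission intensity will be increasing during the period when vaccine is being administered", and says that a rise in anti-AMA1 titre could come from vaccine, natural exposure or both.

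Section 12.5.3 compares study groups by two-sided Fisher's exact tests. Section 12.5.2 describes antibody by vaccine group and time point. Neither mentions cohort.

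**The concern.** Dose and cohort are the same variable apart from the rabies recipients. Anything that differs between early and later volunteers, or between their calendar periods, is attached to dose level. A report repeating the opening of Section 7.1.2 would present 50 v 25 µg as a randomised contrast, which it is not.

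Pooling carries part of the same difference into the comparisons named in the primary objective, because half of each dose group's controls come from the other cohort. The protocol itself predicts a calendar trend. Symptomatic malaria is coded as an adverse event (Section 10.1.1), and fever, headache, malaise and myalgia are solicited (Section 10.1.4). Since the two dose groups are biased in opposite directions against pooled rabies, a cohort shift could look like a dose response. Section 12.5 says that the Day 90 data will inform product development decisions.

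**Working it through.** **Inputs from the plan.** Cohort 1: 20 at 25 µg, 10 rabies. Cohort 2: 20 at 50 µg, 10 rabies (7.1.2). Rabies pooled to 20 (4.3.12). Two-sided Fisher's exact test, unstratified (12.5.3). Lag at least 14 days (6.1).

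**Assumptions.** Level 0.05, since none is stated. Background event rates by cohort are hypothetical; the documents give none. No vaccine or dose effect.

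**1. The plan's own figure.** Table 6 in Section 12.4 is the only sample-size calculation. Pr(0/20) = (1-p)^20 gives 0.818, 0.358, 0.189 and 0.122 at p = 0.01, 0.05, 0.08 and 0.10. The complements are 0.182, 0.642, 0.811 and 0.878. The table reproduces. It concerns a single group of 20 and does not bear on comparisons.

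**2. Where a cohort shift goes.** Let the background mean be m in cohort 1 and m + d in cohort 2.

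- Pooled rabies: [10m + 10(m + d)]/20 = m + d/2.
- 25 µg v pooled rabies: m - (m + d/2) = -d/2.
- 50 µg v pooled rabies: (m + d) - (m + d/2) = +d/2.
- 50 v 25 µg: (m + d) - m = d.
- Either dose v its own cohort's rabies arm: 0.
- All FMP2.1 (40) v all rabies (20): [20m + 20(m + d)]/40 - (m + d/2) = 0.

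The last line shows that the overall comparison is already balanced by cohort.

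**3. Effect on the planned test.** Exact enumeration of Fisher's test, probability of p ≤ 0.05 with no vaccine effect:

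| Background rate, cohort 1 / cohort 2 | 50 v 25 µg | 25 µg v pooled | 50 µg v pooled | 50 µg v own 10 controls |
|---|---|---|---|---|
| 10% / 10% | 0.012 | 0.012 | 0.012 | 0.013 |
| 10% / 20% | 0.072 | 0.028 | 0.032 | 0.022 |
| 20% / 40% | 0.192 | 0.060 | 0.056 | 0.031 |
| 10% / 30% | 0.242 | 0.069 | 0.059 | 0.031 |
| 20% / 50% | 0.409 | 0.108 | 0.085 | 0.026 |

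Fisher's test is conservative at these sizes (about 1% when both rates are 10%), which absorbs much of the half-size bias against pooled rabies. It does not absorb the full bias in 50 v 25 µg.

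**4. Price of concurrent controls.** In units of one SD:

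- Dose v pooled rabies: sqrt(1/20 + 1/20) = 0.316.
- Dose v own rabies: sqrt(1/20 + 1/10) = 0.387. Ratio 0.387/0.316 = 1.22.
- 50 v 25 µg directly: sqrt(1/20 + 1/20) = 0.316.
- 50 v 25 µg as a difference of within-cohort differences: sqrt(2 × 0.15) = 0.548. Ratio 0.548/0.316 = 1.73.
- Fisher power with no cohort shift, 20 v 20 against 20 v 10: 0.908 to 0.736 for 10% v 60%; 0.650 to 0.445 for 20% v 60%.

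**The case against.** Sequential cohorts are inherent in dose escalation, pooling is declared in advance, and Sections 4.3.12 and 12.4 say that only very large differences can be detected. The planned lag is short: at least 14 days, with safety committee calls about two to three weeks after each 25 µg immunization (15.4), at one site. The primary objective compares each dose with rabies, where bias is halved, and does not single out 50 v 25 µg. A final analysis plan is still to be agreed (12.5). All of this stands and limits the size of the point. It does not make the opening of Section 7.1.2 true, and low power does not remove bias. The only content that Section 12.5 names for the later plan is adverse events by dose and number of vaccinations.

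Three stronger readings are tempting:

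- **Large inflation for antibody.** A reader might run a two-sample test on log titre. With an SD of 1 on the ln scale and a 1.5-fold cohort difference, it rejects about 9% of the time for each dose v rabies and 24% for 50 v 25 µg. Section 12.5.2 plans no such test, and neither the SD nor the fold difference is in the documents. A fixed background difference would also largely cancel in fold increases if these are taken from Day 0, although Section 12.5.2 does not name the reference sample. A different rise during follow-up would not cancel. Section 4.3.1 reports serum antibody stable over a season in a perennial-transmission area of Kenya; whether that carries over to seasonal Bandiagara is not shown.
- **Bias in the overall vaccine v rabies comparison.** Both cohorts are 2:1, so there is none, and stratifying that comparison is not a bias remedy.
- **Randomising all 60 to cohort.** This would balance who volunteers early but leave the later dosing of cohort 2 in place. About two weeks of recruitment (15.2.1) plus a 21-day stagger is 14 + 21 = 35 days, the whole screening window.

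**Conclusion.** The point holds in two parts. The contradiction within Section 7.1.2 is certain from the text: dose level and cohort are described as randomised and are assigned by order. The analysis consequence is certain in direction and unknown in size: d in 50 v 25 µg, and -d/2 and +d/2 in the two comparisons with pooled rabies.

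Under the planned Fisher test, a doubling of background rates leaves each dose v pooled rabies at 3-6%, close to the assumed 5%. Clear inflation lies mainly in 50 v 25 µg: 7-19% for a doubling, and 24-41% for the larger assumed gaps of 10% v 30% and 20% v 50%. The shift may be small for local reactions given the short minimum lag; it matters more for antibody titre and for malaria-type symptoms.

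A reader might infer that pooling invalidates the primary safety comparison. The documents do not support that: they give no cohort difference, and moderate assumed ones barely move the planned test. This is a correction of wording plus a missing supporting analysis, and it affects what may be concluded about dose.

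**What to change.** 1. **Correct Section 7.1.2.** State that only FMP2.1 v rabies within a cohort is randomised, that cohort and dose level follow order of enrolment, and that 50 v 25 µg is a non-randomised comparison confounded with cohort.
2. **Keep the pooled-control comparison, and show rabies results by cohort beside it.**
3. **Pre-specify a concurrent-control, cohort-stratified analysis** before unblinding: each dose v its own cohort's rabies arm, for symptoms and for titre change from Day 0. If 50 v 25 µg is discussed, also give the contrast of the two within-cohort differences.
4. **Require any claimed dose or vaccine difference to be consistent with that analysis.**

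No change to enrolment, dosing or the randomisation list is needed. The cost is some added text and tables, and lower precision in the added comparison: a standard error about 22% larger for dose v rabies and about 73% larger for 50 v 25 µg. Because a 20 v 10 comparison is also less sensitive to a real excess of symptoms (Fisher power 0.65 to 0.445 for 20% v 60%), it should accompany the pooled comparison and not replace it.
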